## 5.4 Criteria for Initiation of Study Treatment

The inclusion and exclusion criteria will be checked during Clinical Screening. Eligible subjects will be enrolled prior to the initiation of avelumab and after verification that the subject fulfils all inclusion criteria without meeting any of the exclusion criteria.

## 5.5 Criteria for Subject Withdrawal

### 5.5.1 Withdrawal from the Study

Subjects are free to discontinue the study at any time without giving their reason(s). Withdrawal of consent will be considered withdrawal from the study. In case of withdrawal from the study, the assessments scheduled for the last visit (EOT Visit) should be performed, if possible, with focus on the most relevant assessments (see Section 7.1.3). In any case, the appropriate EOT electronic case report form (eCRF) page must be completed. In case of withdrawal from the treatment, subjects will be asked to continue safety and Long-term Follow-up, which includes the collection of data on survival and subsequent anticancer therapy.

A subject must be withdrawn in the event of any of the following:

- Withdrawal of the subject's consent. If the subject withdraws consent, it must be clearly stated if the subject is also withdrawing their consent from the posttreatment follow-up assessments.
- Participation in any other study during the Treatment Phase of this study; however, subjects will continue to be followed for survival.
- Lost to follow-up.

If a subject will have no further study data collected because he/she withdraws from the study completely or fails to return for visits, the Investigator must determine the primary reason for the subject's withdrawal as completely and accurately as possible and record this information in the eCRF page. For a subject who is "lost to follow-up", the Investigator should show "due diligence" by documenting in the source documents the steps taken to contact the subject, eg, dates of telephone calls, registered letters, etc. Public records may be assessed to determine vital status information (alive/dead) for a subject who is lost to follow-up, as permitted by local laws.

### 5.5.2 Withdrawal from the Investigational Medicinal Product

The subject must be withdrawn from avelumab administration in the event of any of the following:

- Progressive disease (PD) per RECIST 1.1 assessed by Investigator (**Note**: Subjects receiving avelumab may continue past the initial determination of PD if the subject's ECOG performance

status has remained stable, and if, in the opinion of the Investigator, the subject will benefit from continued treatment [see Section 6.2]).

- Significant clinical deterioration (clinical progression) is defined as new symptoms that are deemed by the Investigator to be clinically significant or significant worsening of existing symptoms.
- Occurrence of an exclusion criterion, which is clinically relevant and affects the subject's safety, if discontinuation is considered necessary by the Investigator and/or Sponsor.
- Therapeutic failure requiring urgent additional drug (if applicable).
- Unacceptable toxicity:
  - Occurrence of any Grade  $\geq 4$  ADRs (see Section 5.1.3.1).
  - Occurrence of AEs, resulting in the discontinuation of avelumab being desired or considered necessary by the Investigator and/or the subject (if applicable).
- Occurrence of pregnancy.
- Use of a nonpermitted concomitant drug, as defined in Section 6.5.2, where the predefined consequence is withdrawal from avelumab.
- Withdrawal of the subject's consent to continue avelumab (if a subject withdraws consent, the subject will be asked to continue tumor assessments if RECIST 1.1-defined PD by Investigator does not occur).
- Noncompliance (as defined in Section 6.9).

## 5.6 Premature Termination of the Study

The whole study may be discontinued prematurely in the event of any of the following:

- New information leading to unfavorable risk-benefit judgment of the study drug, eg, due to:
  - Evidence of inefficacy\* of the study drug.
  - Occurrence of significant previously unknown adverse reactions or unexpectedly high intensity or incidence of known adverse reactions.
  - Other unfavorable safety findings\*.

\*Evidence of inefficacy may arise from this study or from other studies; unfavorable safety findings may arise from clinical or nonclinical examinations, eg, toxicology.

- Sponsor's decision that continuation of the study is unjustifiable for medical or ethical reasons.
- Poor enrolment of subjects making completion of the study within an acceptable time frame unlikely.
- Discontinuation of development of the Sponsor's study drug.

Should premature termination of the study occur, the subject should be seen as soon as possible and the same assessments as required for a prematurely withdrawn subject should be performed, as described in Section 7.1.3. The Investigator may be informed of additional procedures to be followed in order to ensure that adequate consideration is given to the protection of the subject's interest.

Health Authorities and Independent Ethics Committees (IECs)/Institutional Review Boards (IRBs) will be informed about the discontinuation of the study in accordance with applicable regulations.

The whole study may be terminated or suspended upon request of the Health Authorities.

## 5.7 Definition of End of Study

If the study is not terminated for a reason given in Section 5.6, the End of Study is defined as the last subject complete 90-day Safety Follow-up Phone Call or the last subject died, whichever comes first.

## 6 Investigational Medicinal Product and Other Drugs Used in the Study

The term IMP refers to the investigational drug undergoing a clinical study, as well as to any comparator drug or placebo (as applicable). In this study, the IMP is avelumab and no comparator drug or placebo is involved.

### 6.1 Description of the Investigational Medicinal Product

Avelumab is a sterile, clear, and colorless solution intended for IV administration. It is presented at a concentration of 20 mg/mL in CCI [REDACTED] and sealed with an CCI [REDACTED].

### 6.2 Dosage and Administration

Subjects will receive an IV infusion of avelumab over 1 hour (- 10 minutes/+ 20 minutes, ie, over 50 to 80 minutes) once every 2 weeks or every week for the first 12 weeks, then starting with Week 13, once every 2 weeks thereafter.

In order to mitigate infusion-related reactions, a premedication regimen of 25 to 50 mg diphenhydramine and 500 to 650 mg acetaminophen (IV or oral equivalent) is mandatory approximately 30 to 60 minutes prior to the first 4 doses of avelumab (see Section 6.4). Premedication should be administered for subsequent avelumab doses based upon clinical judgment and presence/severity of prior infusion reactions. This regimen may be modified based on local treatment standards and guidelines, as appropriate. However, the prophylactic use of systemic corticosteroids is not permitted. Modifications of the infusion rate to be made in the event of infusion-related reactions are described in Section 6.5.5.1.

The starting dose of avelumab is 3 mg/kg (dose escalation according to modified 3 + 3 design up to 20 mg/kg is intended).

The dose of avelumab will be calculated based on the weight of the subject determined within 72 hours prior to the day of drug administration. The dose of avelumab used for the previous administration can be repeated if the change in the subject's weight is < 10% than the weight used for the last dose calculation. Every subject will receive avelumab at the protocol-scheduled dose until confirmed progression by Investigator, significant clinical deterioration (clinical progression), unacceptable toxicity, or until they meet any of the protocol-defined criteria for withdrawal from the study or from avelumab (see Sections 5.5.1 and 5.5.2), or any of the criteria in Section 5.6 are met. Dose modification of avelumab (change in infusion rate) is discussed in Section 5.1.3.

Treatment with avelumab may be continued despite RECIST 1.1-defined progression at any time, if the Investigator considers the subject will continue to receive clinical benefit by continuing treatment with avelumab and if the "Criteria for Continuation of Treatment Beyond Progression" are met.

#### **Criteria for Continuation of Treatment Beyond Progression**

- No new symptoms or worsening of existing symptoms.
- Tolerance to avelumab.
- No decrease in ECOG performance status.
- The Investigator does not consider it necessary to administer a salvage therapy.

If disease progression is due to brain metastasis, subjects may continue avelumab treatment after the local treatment of the brain lesions provided that the above criteria are met in addition to the following and in consultation with the Medical Monitor:

- Brain metastases have been treated locally and are clinically stable for at least 2 weeks prior to re-initiation of treatment with avelumab
- There are no ongoing neurological symptoms that are related to the brain localization of the disease (sequelae that are a consequence of the treatment of the brain metastases are acceptable)
- Subjects must be either off steroids or on a stable or decreasing dose of  $\leq 10$  mg daily prednisone (or equivalent).

In addition, if disease progression is mainly due to a metastatic lesion (nodal or visceral) which in the opinion of the Investigator may be surgically removed or treated with palliative radiation therapy, subjects may continue avelumab treatment after the local treatment of such a lesion provided that:

- It has been at least 2 weeks (post minor surgery) or 4 weeks (post major surgery) and the subject has fully recovered from the surgery.

- It has been at least 2 weeks since the subject's last dose of radiation therapy and any toxicity related to the radiation therapy is recovered to < Grade 2.

The decision to continue treatment should be discussed with the Medical Monitor and documented in the study records. For subjects who continue avelumab beyond RECIST 1.1-defined progression. If discontinuation occurs due to progression and a definitive diagnosis/radiographic confirmation is not made at the time of discontinuation, a second imaging scan may be allowed for confirmation of PD (Confirmed Discontinuation) (see Sections 7.3.3). If PD is not confirmed and the subject wishes to continue study treatment, this will be allowed provided they meet the Criteria for Continuation of Treatment Beyond Progression. Monitoring should continue according to the Schedule of Assessment (Table 1-1 and Table 1-2). Treatment with avelumab should be stopped immediately if the subject does not tolerate avelumab anymore, or if therapeutic failure occurs.

Subjects receiving avelumab who have experienced a CR should be treated for a minimum of 12 months and/or until disease progression or unacceptable toxicity, after confirmation of response.

For subjects who achieve a confirmed CR on avelumab and subsequently develop PD after stopping therapy, but prior to the End of Study (defined in Section 5.7), 1 re-initiation of treatment at the same dose and schedule is allowed at the discretion of the Investigator and with the agreement of the Sponsor Medical Monitor (retreated subjects). To be eligible for retreatment, the subject must not have experienced any toxicity that led to discontinuation of the initial avelumab therapy (see Section 5.5.2). Prior to retreatment, malignant disease must be radiologically re-staged to assess all known sites of the disease and to establish a new baseline for subsequent tumor measurements. Relevant safety laboratory results must also be available and verified prior to retreatment. Retreated subjects will stay on the study and be treated and monitored according to the Clinical Study Protocol.

### 6.3 Assignment to Treatment Groups

Once the subject has provided the signed ICF(s) and has been determined to meet inclusion and exclusion criteria, the Investigator or their delegate will assign a unique Subject Identifier Number and request the study treatment assignment by using the IVRS. Subject Identifiers will comprise 17 digits, the first 10 digits representing the Study Number, the next 3 digits representing the Site Number, and the last 4 digits representing the Subject Number, which will be allocated sequentially starting with 0001. Once the Subject Number is assigned, it must not be reused for any other subject and the Subject Number for that individual must not be changed, even if the subject undergoes re-testing of laboratory parameters that do not meet the inclusion criteria during the 14-day Clinical Screening window (see Section 7.1.1).

If the subject fails to be started on treatment for any reason, the reason and the subject's demographic information should be collected. Other information, such as the reason for not starting treatment, the corresponding eCRF sections should be completed (see Section 7.1.1.1).

The following IMP allocation will be managed manually by Investigator, who assesses how many vials needed for a subject and pick up themselves. The vial number is linked via the GMP qualified system to the corresponding treatment as well as to the subject.

## 6.4 Noninvestigational Medicinal Products to be Used

In order to mitigate infusion-related reactions, a **premedication regimen** of 25 to 50 mg diphenhydramine and 500 to 650 mg acetaminophen (IV or oral equivalent) is mandatory approximately 30 to 60 minutes prior to the first 4 doses of avelumab. This regimen may be modified based on local treatment standards and guidelines, as appropriate. However, the prophylactic use of systemic corticosteroids is not permitted.

Infusion of avelumab will be stopped in case of Grade  $\geq 2$  infusion-related, allergic, or anaphylactic reactions. Following avelumab infusion, subjects must be observed for 2 hours after the infusion for potential infusion-related reactions.

If an allergic reaction occurs, the subject must be treated according to the best available medical practice. Guidelines for the management of infusion-related reactions are provided in Section 6.5.5.1. Subjects should be instructed to report any delayed reactions to the Investigator immediately.

## 6.5 Concomitant Medications and Therapies

### 6.5.1 Permitted Medicines and Therapies

Any medications (other than those excluded by the Clinical Study Protocol) considered necessary for the subjects' welfare and which will not interfere with avelumab may be given at the Investigator's discretion.

The Investigator will record all concomitant medications taken by the subject during the study, from the date of signature of informed consent, in the appropriate section of the eCRF.

Medications other than those specifically excluded in this study (see Section 6.5.2) may be administered for the management of symptoms associated with the administration of avelumab as required. These might include analgesics, anti-nausea medications, antihistamines, diuretics, anti-anxiety medications, and medications for pain management, including narcotic agents.

Any additional concomitant therapy that becomes necessary during the study and any change to existing concomitant drugs must be recorded in the corresponding section of the eCRF, noting the name, dose, duration, and indication of each drug.

Palliative bone-directed radiotherapy (eg, local radiotherapy for analgesic purposes or for lytic lesions at risk of fracture) may be administered during the study. The assessment of PD will be made according to RECIST 1.1 (Section 12, Appendix II) and not based on the necessity for palliative bone-directed radiotherapy. Bone-directed radiotherapy should be within a limited field

of radiation and for palliation only; the course should be short, according to local institutional recommendation.

Rescue medications may be administered to address ineffective treatment, anticipated adverse reactions, or anticipated emergency situations.

## 6.5.2 Prohibited Medicines

As stated in the exclusion criteria (Section 5.3.2), subjects must not have had prior therapy with any antibody or drug targeting T cell coregulatory proteins (immune checkpoints) such as PD-1, PD-L1, CTLA-4, 4-1BB, LAG 3, TIM 3 or anti-CD127, or concurrent anticancer treatment (eg, cytoreductive therapy, radiotherapy [with the exception of palliative bone-directed radiotherapy, and radiotherapy administered to superficial lesions], immune therapy, or cytokine therapy except for erythropoietin), major surgery (excluding prior diagnostic biopsy), concurrent systemic therapy with steroids or other immunosuppressive agents, or use of any investigational drug within 28 days before the start of study treatment.

In addition, the following treatments must not be administered during the study:

- Immunotherapy, immunosuppressive drugs, ie, chemotherapy or systemic corticosteroids except:
  - When required for the treatment of irAEs or infusion-related reactions / hypersensitivity.
  - Systemic corticosteroids at physiologic doses  $\leq 10$  mg/day of prednisone or equivalent.
  - Systemic corticosteroids for management of patients with allergy to CT Intravenous Radiographic Contrast Media.
- Any vaccine therapies for the prevention of infectious disease (eg, seasonal influenza vaccine, human papilloma virus vaccine) except administration of the inactive vaccine.
- Growth factors (granulocyte colony stimulating factor or granulocyte macrophage colony stimulating factor). Exception: erythropoietin and darbepoetin alpha may be prescribed at the Investigator's discretion.

If the administration of a nonpermitted concomitant drug becomes necessary during the study, the subject will be withdrawn from treatment with avelumab (see Section 5.5.2). The Sponsor may be contacted to discuss whether avelumab must be discontinued.

### 6.5.2.1 Clarification of Corticosteroid Use

Data indicate that corticosteroids may inhibit and interfere with T cell function (Schleimer et al 1984; Khan 2008). Furthermore, as with all immunotherapies intended to augment cell-mediated immunity, there is a risk that concomitant immunosuppressive agents such as corticosteroids will counteract the intended benefit. However, studies with anticytotoxic T-lymphocyte antigen-4 compounds indicate that short-term use of steroids can be employed without compromising

clinical outcomes (Weber et al 2012). Therefore, the use of corticosteroids during this study is restricted as follows:

- Therapeutic use: limited to the treatment of infusion-related reactions and short-term treatment of irAEs. The course of corticosteroid treatment should be completed as soon as clinically feasible and before resuming the next cycle of avelumab provided the event has resolved to a Grade 1 or less.
- Physiologic use: replacement for adrenal insufficiency at doses equivalent to  $\leq 10$  mg prednisone daily are acceptable.
- Prophylactic use: prophylactic use, eg, for the prevention of acute infusion-related reactions, constitutes concomitant use and is prohibited.

### 6.5.3 Other Nonpermitted Interventions

The following nondrug therapies must not be administered during the study:

- Radiotherapy (except for palliative bone-directed radiotherapy [see Sections 5.3.2 and 6.5.1] or radiotherapy administered to superficial lesions).
- Herbal remedies with immunostimulating properties (eg, mistletoe extract) or known to potentially interfere with major organ function (eg, hypericin).
- Traditional Chinese medicine that has an approved indication in treating cancer from the China Food and Drug Administration.

### 6.5.4 Special Precautions

As a routine precaution, subjects enrolled in this study must be observed for 2 hours after the infusion of avelumab in an area with resuscitation equipment and emergency agents. At all times during study treatment, immediate emergency treatment of an infusion-related reaction or a severe hypersensitivity reaction according to institutional standards must be assured. In order to treat possible anaphylactic reactions, for instance, dexamethasone 10 mg and epinephrine in a 1:1000 dilution or equivalents should always be available along with equipment for assisted ventilation. Please also refer to Section 6.4.

Infusion of avelumab will be stopped in case of  $\geq$  Grade 2 hypersensitivity, inflammatory response, or anaphylactic reaction. The treatment recommendations for infusion-related reactions, according to the NCI are outlined in Section 6.5.5.1. All infusion-related reactions occurring during the infusion of avelumab or within 2 hours after completion of the administration of avelumab should be reported as irAEs.

Investigators should also monitor subjects closely for potential irAEs, which may manifest at the earliest after weeks of treatment. Such events may consist of persistent rash, diarrhea and colitis, autoimmune hepatitis, arthritis, glomerulonephritis, cardiomyopathy, or uveitis and other inflammatory eye conditions.

## **6.5.5 Management of Specific Adverse Events or Adverse Drug Reactions**

### **6.5.5.1 Infusion-related Reactions**

In order to mitigate infusion-related reactions, patients have to be premedicated with an antihistamine and with paracetamol (acetaminophen) prior to the first 4 infusions of avelumab. Premedication should be administered for subsequent avelumab doses based upon clinical judgment and presence/severity of prior infusion reactions.

Management of infusion-related reactions should follow guidelines set forth in [Table 6-1](#).

**Table 6-1 Management of Hypersensitivity and Infusion-related Reactions Caused by Avelumab**

NCI-CTCAE Grade	Treatment Modification for Avelumab
Grade 1: Mild Mild transient reaction; infusion interruption not indicated; intervention not indicated	
 
Decrease avelumab infusion rate by 50% and monitor closely for any worsening.
 

Grade 2: Moderate Therapy or infusion interruption indicated but responds promptly to symptomatic treatment (eg, antihistamines, nonsteroidal antiinflammatory drug, narcotics, intravenous fluids); prophylactic medications indicated for ≤ 24 hours	
 
Temporarily discontinue avelumab infusion
 
Resume infusion at 50% of previous rate once infusion-related reaction has resolved or decreased to at least Grade 1 in severity and monitor closely for any worsening.
 

Grade 3 or Grade 4: Severe or Life-threatening Grade 3: Prolonged (eg, not rapidly responsive to symptomatic medication and/or brief interruption of infusion); recurrence of symptoms following initial improvement; hospitalization indicated for clinical sequelae Grade 4: Life-threatening consequences; urgent intervention indicated	
 
Stop the avelumab infusion immediately and disconnect infusion tubing from the subject
 
Subjects have to be withdrawn immediately from avelumab treatment and must not receive any further avelumab treatment.
 

NCI-CTCAE: National Cancer Institute-Common Terminology Criteria for Adverse Events.

Once the avelumab infusion rate has been decreased by 50% or interrupted due to an infusion-related reaction, it must remain decreased for the next scheduled infusion. If no infusion-related reaction is observed in the next scheduled infusion the infusion rate may be returned to baseline at the all subsequent infusions. If an infusion reaction occurs, all details about drug preparation and infusion must be recorded.

Subjects should be instructed to report any delayed reactions to the Investigator immediately.

### Additional Modification for Subjects with Grade 2 Infusion-related Reactions

If, in the event of a Grade 2 infusion-related reaction that does not improve or worsens after implementation of the modifications indicated in Table 6-1 (including reducing the infusion rate by 50%), the Investigator may consider treatment with corticosteroids and the infusion should be stopped for that day. At the next cycle, the Investigator may consider the addition of H2-blocker antihistamines (eg, famotidine or ranitidine), meperidine or ibuprofen in addition to the mandatory premedication, for selected subjects. However, prophylactic steroids are **NOT** permitted (please refer to Section 6.5.2.1).

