### Dose-limiting Toxicity

A DLT is defined as a  $\geq$  Grade 3 ADR according to the NCI-CTCAE v4.03, occurring during the DLT observation period of the dose escalation cohorts. An ADR is defined in this study as any AE suspected to be related to avelumab by the Investigator and/or Sponsor. A DLT must be confirmed by the SMC as being related to avelumab.

A DLT is specifically defined as any Grade  $\geq$  3 toxicity that is possibly, probably, or definitely related to avelumab, occurring during the DLT observation period, except for any of the following:

- Grade 3 infusion-related reaction resolving within 6 hours and controlled with medical management.
- Transient ( $\leq$  6 hours) Grade 3 flu-like symptoms or fever, which is controlled with medical management.
- Transient ( $\leq$  24 hours) Grade 3 fatigue, local reactions, headache, nausea, emesis that resolves to  $\leq$  Grade 1.
- Grade 3 skin toxicity, or Grade 3 LFT (ALT, AST, or gamma-glutamyl transferase) increase that resolves to  $\leq$  Grade 1 in less than 7 days after medical management (eg, immunosuppressant treatment) has been initiated.
- Grade 3 diarrhea unless to be discontinued according to Treatment Guidelines. In this case it would be an DLT again.
- Single laboratory values out of normal range that are unlikely to be related to avelumab according to the Investigator, do not have any clinical correlate, and resolve to  $\leq$  Grade 1 within 7 days with adequate medical management.
- Tumor flare phenomenon defined as local pain, irritation, or rash localized at sites of known or suspected tumor.

The ADRs (including DLTs) that require permanent discontinuation of avelumab are described in Section 5.1.3.1.

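### Section 6.5.5.1 gives two incompatible instructions on further avelumab after an infusion reaction that does not respond to interruption, or that returns after the half-rate restart: a same-day stop as Grade 2, or permanent withdrawal as Grade 3 under Table 6-1

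*Protocol*

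**What the plan says.** Table 6-1 in Protocol Section 6.5.5.1 sets out grades and actions for infusion-related reactions.

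- Grade 2 is described as "Therapy or infusion interruption indicated but responds promptly to symptomatic treatment". The action is to interrupt and then: "Resume infusion at 50% of previous rate once infusion-related reaction has resolved or decreased to at least Grade 1 in severity".
- Grade 3 is described as "Prolonged (eg, not rapidly responsive to symptomatic medication and/or brief interruption of infusion); recurrence of symptoms following initial improvement", among other features. For Grades 3 and 4 the action reads: "Subjects have to be withdrawn immediately from avelumab treatment and must not receive any further avelumab treatment".

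The paragraph on additional modifications that follows applies "in the event of a Grade 2 infusion-related reaction that does not improve or worsens after implementation of the modifications indicated in Table 6-1", and counts the 50% rate reduction among those modifications. It lets the investigator consider corticosteroids, then says "the infusion should be stopped for that day. At the next cycle, the Investigator may consider the addition of" further medicines for selected subjects. It does not refer to the Grade 3 row.

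Section 7.4.1.1 sets the DLT threshold at Grade 3 or higher under NCI-CTCAE v4.03 and exempts a "Grade 3 infusion-related reaction resolving within 6 hours and controlled with medical management".

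**The concern.** The additional paragraph starts where the Grade 2 row of Table 6-1 has failed, yet it keeps the Grade 2 label. In the two clearest cases that failure is what Table 6-1 uses to describe Grade 3. An investigator with such a subject can follow one text and plan the next infusion, or follow the other and never dose the subject again.

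The main stake is subject safety and uniform conduct: whether a subject is re-exposed depends on which paragraph the site reads. This applies in all cohorts, including the 10 mg/kg once weekly cohort. Infusion-related reactions are one of the two primary identified risks in Section 3.4, so the case is foreseeable.

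The second stake is narrower. The SAP (Section 15.1) takes DLT data from the adverse event form. If the site enters the Grade 2 label there, the event may not be put forward as a possible DLT.

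**Working it through.** No published figure has to be reproduced; the check is a comparison of texts, followed through to the DLT rules.

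**Step 1. Which events fall under both texts?**

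| Course of a reaction first graded 2 | Additional paragraph | Table 6-1 wording |
|---|---|---|
| Does not respond to the interruption | Grade 2, stop for the day, next cycle foreseen | Fits the Grade 3 description (slow to respond to brief interruption): withdraw |
| Falls to Grade 1 or resolves, restart at 50% rate, symptoms return | Grade 2, stop for the day, next cycle foreseen | Fits the Grade 3 description (return after improvement): withdraw |
| Falls to Grade 1, restart at 50% rate, mild residual symptom unchanged | Arguably has not improved, so may be covered | Need not meet the Grade 3 description |

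The second row follows from Table 6-1 itself. Restart is allowed only once the reaction has eased, so symptoms that come back at the half rate have come back after improvement. The first two rows conflict; the third does not.

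**Step 2. Does another section settle it?** No. Section 5.1.3.1 sends infusion reactions back to Section 6.5.5.1. The list of reasons to withdraw from avelumab in Section 5.5.2 names Grade 4 or higher drug reactions but not a Grade 3 infusion reaction. SAP Appendix 18.1 has a deviation code for continuing after a Grade 4 or higher drug reaction (PDEV07), and none for continuing after a Grade 3 infusion reaction.

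**Step 3. Consequence for the DLT endpoint.** Take one avelumab-related event within 21 days in a DLT-evaluated subject.

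- Recorded as Grade 2: below the DLT threshold.
- Recorded as Grade 3, lasting over 6 hours or not controlled: a DLT candidate, subject to SMC confirmation.
- Recorded as Grade 3, resolved within 6 hours and controlled: exempt. If the subject is withdrawn after dose 1, the subject has neither had every dose due in the window nor stopped because of a DLT. The subject then leaves the DLT Analysis Set (Protocol Section 8.4, SAP Section 8.2) and may be replaced (Section 5.1.1.1).

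Under Section 5.1.2.1.2 one event can matter. At 3 or 20 mg/kg, 0/3 becomes 1/3, and the decision then rests on 6 DLT-evaluated subjects. At 10 mg/kg every 2 weeks, 1/6 becomes 2/6, which changes escalation into a hold.

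**Step 4. Who is affected.** The DLT consequence does not reach the once weekly cohort, which has no DLT assessment. Nor does it reach the three subjects added at 20 mg/kg for PK after 0/3 DLTs. The conflict over re-exposure reaches everyone.

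**Step 5. Illustration only.** The text available gives no rate for a non-responding or recurring reaction that lasts over 6 hours or is not controlled (part of Section 3.2.1 was not available). Let p be an assumed per-subject probability of such an event in the DLT window.

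P(at least 1 of 3) = 1 − (1 − p)³

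P(at least 2 of 6) = 1 − (1 − p)⁶ − 6p(1 − p)⁵

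| p (assumed) | At least 1 of 3 | At least 2 of 6 |
|---|---|---|
| 1% | 3.0% | 0.15% |
| 5% | 14.3% | 3.3% |
| 10% | 27.1% | 11.4% |

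These are chances that the event occurs, not that it is missed. The only related figure found is 3 of 1300 subjects (0.2%) with a Grade 4 infusion reaction in Section 3.4, before premedication became mandatory. That is a different event and does not fix p.

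**The case against.** The strongest reply is that the additional paragraph sets management and assigns no grade. It opens with a condition. Grading is fixed elsewhere: the investigator grades every adverse event by NCI-CTCAE v4.03 and a DLT is defined on that scale (Section 7.4.1.1), the SMC decides on DLTs (Section 2.1), and SAP Section 15.2.1 already tabulates worst severity per subject. This stands. A reader might infer that a reaction handled under the paragraph can never be a DLT, and that all such events are lost from the DLT count. The documents do not support that, because the grade on the form does not depend on the paragraph followed and SMC review comes after it. What remains is a risk. Worst-severity tables cannot correct a grade entered too low, and the SMC confirmation in Section 7.4.1.1 concerns relatedness to avelumab.

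A reader might also infer that every event under the paragraph is Grade 3 by Table 6-1. The residual Grade 1 case shows otherwise, and the Grade 3 description gives an example and no time limit, which leaves room for judgment. That narrows the overlap to the first two rows in Step 1 without removing it.

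Finally, the paragraph does not order re-dosing; its next-cycle measures are optional and for selected subjects. That is correct. Even so, foreseeing a next cycle cannot be squared with a rule that allows none.

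**Conclusion.** The contradiction is real and should be corrected. For a reaction that does not respond to the interruption, or that returns after the half-rate restart, Section 6.5.5.1 both foresees a next cycle and, through the Grade 3 row of Table 6-1, excludes one. This holds in all cohorts and rests only on the two texts.

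The effect on the primary endpoint is secondary and conditional. It needs an event in the 21-day window of a DLT-evaluated subject on the every-2-weeks schedule, a Grade 2 label carried onto the adverse event form, and no correction by CTCAE grading or SMC review. For a missed DLT, the reaction must also last over 6 hours or be uncontrolled. If all of that happens, one event is enough to change a cohort decision. How often it would happen cannot be derived from the documents, and the 1% to 10% range is an assumption.

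**What to change.** 1. Reconcile Table 6-1 and the additional-modification paragraph in Section 6.5.5.1, so that a reaction that does not respond to interruption, or returns after the 50% rate restart, has one grade and one instruction. Say also how a mild residual symptom after restart is to be handled. Which rule applies is for the sponsor's clinicians.
2. Add one sentence to Section 7.4.1.1: the DLT decision uses the worst NCI-CTCAE v4.03 grade over the whole infusion-reaction episode, whichever management paragraph was followed. The TEAE tables need no new rule, since SAP Section 15.2.1 already uses worst severity.

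The cost is one paragraph and one sentence of protocol text, handled under the amendment procedure in Section 10.5, with no new data collection. The count of Grade 3 or higher infusion reactions in SAP Section 15.2.5 may rise slightly where sites would otherwise have entered Grade 2.
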